6.8.7.2 Reporting Serious Unexpected Suspected Adverse Reactions (SUSARs)

The Investigator must immediately report SUSARs that occur or are observed during the course of the study or within 30 days of the subject's last study visit. In the event of a SUSAR, the site must notify the Medical Monitors for the study (contact information in Section 6.8.7.1) using the SAE report form within 24 hours of notification, observation, or occurrence of the SUSAR, whether or not complete information is available. In the case of incomplete information, the Investigator must provide follow-up information as soon as possible using the SAE report form. If the event is reported outside of regular business hours and collected by Trial Runners, their Medical Monitor will notify the Sponsor Medical Monitor within 24 hours of knowledge of the event (contact information in Section 6.7.8.1).

Reports will be evaluated by the Medical Monitor. The IRB/IEC and Investigators at other study sites will be informed as required.

6.9 Concomitant Medication Assessments

Use of any medication – prescription or over-the-counter (OTC) should be recorded at the screening visit, and captured on the appropriate CRF, and the indication noted as part of the medical history. Treatments that are permitted to continue throughout the duration of the study will be recorded as concomitant medications at all subsequent visits. Judgment of continued study participation by the subject, and inclusion of this subject's subsequent visits in the safety and efficacy analysis will be made by the Investigator.

All medications which the subject has taken within 30 days prior to screening and during the study will be recorded in the CRF. The name of the drug, dose, route of administration,

duration of treatment and indication will be recorded for each medication. For combination products (e.g., CONTAC®), the brand name is required. For non-combination products, the generic name is preferred. The use of routine ophthalmic diagnostic pharmaceutical agents (e.g., fluorescein) will be allowed, and individual documentation not required. However, medications used as part of the intravitreal injection process other than topical or subconjunctival anesthetic and povidone iodine swabs (e.g. pre-or post-injection antibiotics or IOP-lowering medications) should be recorded on the CRF. Any change in dosing parameters should also be recorded in the CRF.

6.10 Removal of Subjects from the Study or Investigational Product

Subjects may be discontinued from the study at any time for any reason. Removal of the investigational product should not be necessary, but if it is, it will be performed by vitrectomy, and the subject will be informed of this during the Consent process. Participation is entirely voluntary, and only possible if the subject has signed informed consent. Consent may be withdrawn at any time.

6.10.1 Completed Subject

A completed subject is defined as one who completes all visits planned through the completion of the Month 6 visit procedures.

6.10.2 Non-Completing Subject

A non-completing subject is defined as one who exits the study by their own volition or at the discretion of the Investigator and/or the study Medical Monitor. Any subject may decide to voluntarily withdraw from the study at any time without prejudice. In this event, Investigator will make every attempt to complete all assessments scheduled for the final (Month 6) visit.

6.11 Appropriateness of Measurements

The ophthalmic and systemic measures included in this study are consistent with standard of care.

7. STUDY ACTIVITIES

A detailed Schedule of Visits and Procedures is provided in [Table 1](#).

7.1 Screening Visit (Visit 1, █ to -1)

This visit may take place at any time of the day.

Adult subjects (18 years or older) with decreased VA as a result of clinically-detectable ME secondary to BRVO or CRVO are eligible for this study. Potential subjects will arrive at the Investigator's office and be interviewed by a member of staff regarding their eligibility for the study. Individuals will be presented with the informed consent form (ICF) and asked to

review it and discuss as needed with site staff, family or friends and return to the site to sign the form. Once informed consent has been obtained, the Screening visit can continue.

The subject's demographic and medical history will be collected, and a record made of their current and recent medication use. Vital signs will be collected and documented. Blood samples will be collected and if the subject is a female deemed to be of child-bearing potential, a urine pregnancy test will be administered. Male subjects with female partners of child-bearing potential should agree to comply with the guidelines on acceptable birth control described in [Exclusion criterion # 23](#).

Ocular assessments will be performed on both eyes (OU) unless otherwise noted. The following ocular assessments will be performed prior to pupil dilation (mydriasis):

- BCVA using the ETDRS method and following manifest refraction
- Slit-lamp biomicroscopic examination
- Gonioscopy
- IOP measured using a Goldmann applanation tonometer.

Following mydriasis, the following procedures will be performed OU unless otherwise noted:

- SD-OCT
- Fundus examination
- 3-field fundus photography
- Fluorescein angiography

The subject will then schedule their return visit when their laboratory tests and Reading Center assessments will be available to the Investigator prior to randomization. The subject will be allowed to leave the office on condition that they have help and/or transportation to return home since they will have undergone pupil dilation.

7.2 Treatment Period

7.2.1 Visit 2 (█) Procedures

This visit may take place at any time of the day.

The subject will be queried regarding any changes to their ocular or medical health status since the previous visit, and also if there have been any changes to their ongoing medications or procedures. Vital signs (heart rate and blood pressure) will be collected. The Investigator should go over the results from the Reading Center and the clinical chemistry and hematology values with the subject.

The following ocular assessments will be performed OU prior to pupil dilation:

- BCVA using the ETDRS method and following manifest refraction
- Slit-lamp biomicroscopic examination
- Goniscopy
- IOP measured using a Goldmann applanation tonometer

Following mydriasis, the following procedures will be performed OU:

- SD-OCT
- Fundus examination
- 3-field fundus photography
- Fluorescein angiography

If the subject is deemed to be still eligible to enroll in the study in the Investigator's opinion, trained personnel will prepare the implant and applicator, and administer the implant following the directions provided in the MoP. Following administration, the subject should be monitored to ensure their retinal circulation returns to normal, their optic disc is perfused and their IOP returns to baseline (pre-administration) levels.

7.2.2 Visit 3 (████████ ± 2 days) Procedures (also applies to Visit 3b, (████████ 2 days, ████████))

At this visit, the subject will be queried regarding any changes to their ocular or medical health status since the previous visit, and also if there have been any changes to their ongoing medications or procedures. Vital signs (heart rate and blood pressure) will be collected.

The following procedures will be performed OU:

- BCVA by ETDRS will be conducted following manifest refraction
- Slit-lamp biomicroscopy examination
- IOP measured using a Goldmann applanation tonometer

Following mydriasis, the following procedures will be performed OU, unless otherwise noted:

- Fundus examination
- The implant will be viewed to verify its status (study eye only)

7.2.3 Visits 4 and 5 ([REDACTED] ± 3 Days) and Visits 7 and 8 ([REDACTED] ± 3 Days) Procedures

At these visits, the subject will be queried regarding any changes to their ocular or medical health status since the previous visit, and also if there have been any changes to their ongoing medications or procedures. Vital signs (heart rate and blood pressure) will be collected. Blood samples will be collected (Month 1 and Month 2 visits only) for laboratory assessment of clinical chemistry and hematology.

The following assessments will be conducted OU:

- BCVA by ETDRS will be conducted following manifest refraction
- Slit-lamp biomicroscopy
- IOP measured using a Goldmann applanation tonometer

Following mydriasis, the following procedures will be performed OU, unless otherwise specified:

- SD-OCT (study eye)
- Fundus examination
- The implant will be viewed to verify its status. (study eye)

7.2.4 Visit 6 ([REDACTED] ± 3 Days) and Visit 9 ([REDACTED] ± 3 Days) Procedures

At these visits, the subject will be queried regarding any changes to their ocular or medical health status since the previous visit, and also if there have been any changes to their ongoing medications or procedures. Vital signs (heart rate and blood pressure) will be collected.

Blood samples will be collected for laboratory assessment of clinical chemistry and hematology and if the subject is a female of child-bearing potential, a urine pregnancy test should be administered (Visit 9 only).

The following procedures will be conducted OU:

- BCVA by ETDRS will be conducted following manifest refraction
- Slit-lamp biomicroscopy examination
- Gonioscopy (study eye)
- IOP measured using a Goldmann applanation tonometer

Following mydriasis, the following procedures will be performed OU unless otherwise noted:

- SD-OCT (study eye)
- Fundus examination (study eye)
- Fluorescein angiography
- 3-field fundus photography (study eye)
- The implant will be viewed to verify its status (study eye)

If residual implant is still visible in the vitreous at the Month 6 visit, the subject will be required to return to the site at Month 7 for safety follow-up. Otherwise, the Month 6 visit will be the final visit, and the subject should be thanked for their participation in the study.

7.3 [REDACTED] or Early Termination Procedures

Procedures that should be conducted in the event that the subject needs to exit the study prior to Month 6 (Visit 9) are provided above in Section [7.2.4](#).

7.4 Follow-up Visits ([REDACTED] ± 3 days as required for residual implant assessment)

Monthly safety visits should be scheduled if, following the assessments at Month 6 (Visit 9) are completed, it is noted that the vitreous still contains visible implant. At these visits, the subject will be queried regarding any changes to their ocular or medical health status since the previous visit, and also if there have been any changes to their ongoing medications or procedures. Vital signs (heart rate and blood pressure) will be collected.

The following procedures will be conducted OU:

- BCVA by ETDRS following manifest refraction
- Slit-lamp biomicroscopy examination
- IOP measured using a Goldmann applanation tonometer

Following mydriasis, the following procedures will be performed in the study eye:

- SD-OCT
- Fundus examination
- 3-field fundus photography
- The implant will be viewed to verify its status

If necessary, a second follow-up visit will be scheduled. The format of this follow-up visit should continue until either the subject requires re-treatment (i.e. standard of care rescue treatment), or until 1 month after no residual implant is observed, or to Month 9, whichever comes first, at which point the subject will exit the study.

8. QUALITY CONTROL AND ASSURANCE

The progress of the study will be monitored by on-site, written, and telephone communications between personnel at the Investigator's site and the Study Monitor. The Investigator will allow the Sponsor or designee to inspect all CRFs; subject records (source documents); signed consent forms; records of study medication receipt, storage, preparation, and disposition; and regulatory files related to this study.

9. PLANNED STATISTICAL METHODS

9.1 General Considerations

All continuous study assessments will be summarized by treatment [and phase (initial vs. randomized) for CF1] and visit (as applicable) using descriptive statistics (n, mean, median, standard deviation, minimum, and maximum). All categorical study assessments will be summarized by treatment and visit (as applicable) using frequency counts and percentages.

All study data will be listed by treatment [and phase (initial vs randomized) for CF1], patient and visit (as applicable).

The unit of analysis for efficacy will be the study eye.

Statistical methods will be more fully described in separate document(s) (i.e., the Statistical Analysis Plan).

9.2 Determination of Sample Size

This study is not powered to detect a pre-stated efficacy signal, but rather will be used to inform the design and power for future studies. With a sample size of 20 evaluable subjects per treatment group, the study will have 95% confidence of ruling out AEs with true incidence rates of 13.9% or higher within each treatment group. That is, with 20 subjects in a treatment group, if an AE of a specific type is not observed, then with 95% confidence, the true incidence rate of that adverse event is less than 13.9%.

9.3 Analysis Populations

9.3.1 Safety Population

The safety population will include all subjects who received study medication. This population will be used to summarize safety variables and will summarize subjects as treated.

9.3.2 Intent-to-Treat (ITT) Population

The ITT population will include all subjects who received study medication. This population will be the primary population for efficacy analyses and will be used to summarize all efficacy variables and will summarize subjects as treated.

9.3.3 Per Protocol (PP) Population

The PP population is a subset of the ITT population, which will include those subjects who do not have major protocol violations likely to seriously affect the efficacy outcomes of the study. This population will be the secondary population for efficacy analyses and will be used to summarize a subset of efficacy variables. If the PP and ITT populations are exactly the same, then additional efficacy analyses on the PP population will not be performed. The PP population will summarize subjects as treated.

9.4 Demographics and Baseline Characteristics

Demographic and baseline characteristics such as age, gender, race, and ethnicity will be summarized and listed. Medical history, history of ocular surgery and procedures, and RVO history will also be summarized and listed.

9.5 Primary Safety Assessments and Analyses

The primary safety analysis will summarize ocular and non-ocular treatment-emergent adverse events (TEAEs) using discrete summaries at the subject level by system organ class and preferred term for each treatment group. Ocular TEAEs will be summarized separately for all study and fellow eyes. A TEAE will be defined as occurring after the first dose of study medication. Serious adverse events and treatment-related ocular and non-ocular TEAEs will be summarized similarly. Ocular and non-ocular TEAEs will also be summarized by severity.

Slit lamp biomicroscopy and dilated indirect ophthalmoscopy measures will be summarized at each visit using discrete summary statistics.

Intraocular pressure will be summarized at each visit, using continuous and discrete summary statistics, including change from baseline and the proportion of study eyes with an increase from baseline in IOP of 10 mmHg or more and the proportion of study eyes with IOP of 30 mmHg or more.

Vital signs and safety laboratory data will be summarized at each visit, using continuous summary statistics, including change from baseline.

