Within the last 10 years, intravitreal pharmacotherapy has revolutionized the therapeutic options for ME-associated retinal vascular diseases, and particularly for RVO. Current options for treating ME depend upon the cause and severity of the condition. In the case of RVO, the goal is to reduce the amount of fluid leakage and decrease the edema, thus leading to improved visual acuity (VA). Argon laser photocoagulation was used for many years to treat ME associated with BRVO, but was less effective in the treatment of CRVO, and was not successful in all patients ([Fekrat 1997](#)). Currently, two classes of medication are approved to treat ME following RVO – corticosteroids (such as OZURDEX® dexamethasone intravitreal implant), and more recently, anti-vascular endothelial growth factor (VEGF) therapies such as ranibizumab (LUCENTIS®) and afibbercept (EYLEA®). The anti-VEGFs, while effective at modulating vascular permeability, do not address the inflammatory component of RVO however. Corticosteroids have the advantage of targeting the three components of the pathophysiology of RVO; reducing ME through inhibition of multiple inflammatory mediators, stabilizing the blood brain barrier and decreasing vascular permeability ([Zas 2017](#), [OZURDEX PI](#)). Corticosteroids such as dexamethasone (OZURDEX) and triamcinolone (KENALOG®) have demonstrated ME reduction and improvement in VA when dosed intravitreally ([Cekic 2005](#), [Ip 2003](#), [OZURDEX PI](#)). OZURDEX (0.7 mg dexamethasone) intravitreal implant has been evaluated in RVO and demonstrated efficacy up to 6 months ([Haller 2010](#)), although the peak efficacy is generally achieved by Month 3 ([Joshi 2013](#), [Bandello 2015](#)).

While both classes of medication have demonstrated efficacy in RVO patients, the treatment burden is high, with the anti-VEGFs typically requiring monthly ([LUCENTIS PI](#), [EYLEA PI](#)) intravitreal injections, and the dexamethasone intravitreal implant typically requiring re-injection every 3 months ([Bezatis 2013](#), [Augustin 2014](#)). A corticosteroid implant that offered a longer duration of effect would provide the benefit of reducing the

treatment burden on patients while treating the inflammatory components of ME that are not addressed by inhibition of VEGF.

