3. INVESTIGATIONAL PLAN

3.1 Overall Study Design and Plan

This will be a 6-month (with follow-up, if necessary, to monitor residual implant), open-label, multicenter study evaluating the safety, tolerability, and efficacy of 2 formulations of dexamethasone intravitreal implant, AR-1105, in a single eye of up-to 45 subjects between 18 and 80 years of age with ME secondary to RVO.

Data collected through Month 6 on the safety and tolerability of each formulation, as well as efficacy signals for each subject randomized, will be used to determine which formulation will be selected for further clinical development. Any subject who presents at Month 6 with

[figure not shown]
visible residual implant will be followed until they require retreatment (following the criteria provided for rescue therapy), or until 1 month after the implant is no longer visible or to Month 9, whichever occurs first.

Rescue therapy in the form of standard of care will be offered to any subject who, in the opinion of the investigator, requires additional therapy for their RVO due to lack of efficacy after Month 3/Week 12. Minimum guideline criteria for consideration of rescue are an increase in CRT of 50 μ m and decrease in BCVA of ≥ 7 letters at any time compared to baseline.

In the case of elevated IOP or cataract, investigators should treat the subject according to standard practice. In the case of a cataract, removal should be performed as soon as possible since BCVA could be impacted by the cataract.

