4.1 Method of Assigning Subjects to Treatment Groups

Providing none of the subjects experience any clinically-meaningful ocular adverse reactions (possibly) related to treatment with AR-1105 during the initial phase, the study will continue into the randomized phase. During the randomized phase of the study, subjects will be assigned in a 1:1 ratio to either AR-1105-CF1 or AR-1105-CF2.

5. Sample Size and Power Considerations

This study is not powered to detect a pre-stated efficacy signal, but rather will be used to inform the design and power for future studies. With a sample size of 20 evaluable subjects per treatment group, the study will have 95% confidence of ruling out adverse events (AE) with true incidence rates of 13.9% or higher within each treatment group. That is, with 20 subjects in a treatment group, if an AE of a specific type is not observed, then with 95% confidence, the true incidence rate of that AE is less than 13.9%.

6. Data Preparation

All reported study data will be recorded on the electronic case report forms (eCRF) supplied by Statistic & Data Corporation (SDC). Only the Principal Investigator and authorized study staff according to the Delegation of Responsibilities log are entitled to make entries in the eCRF.

After data are entered into the clinical study database, electronic edit checks and data review will be performed. All data validation specifications and procedures are detailed in the Data Validation Manual as a separate document. When the database has been declared to be complete and accurate, the database will be locked. Any changes to the database after data have been locked can only be made with the approval of the Sponsor and Trial Runners in consultation with SDC.

The final analyses outlined in this document will be carried out after the following have occurred:

- All data management requirements are met according to SDC standard operating procedures, including data entry, performance of edit and validation checks, documentation and resolution of data queries, and database lock with written authorization provided by appropriate SDC and Sponsor personnel.
- Protocol deviations have been identified and status defined (major/minor deviations).
- Analysis populations have been determined.

7. Analysis Populations

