Example SAS codes: PROC LIFETEST Data=xxx method=KM;

Strata treatment/test=logrank;

Time AVAL*CENSOR(0);

Run;

where CENSOR indicates censored subjects.

PROC PHREG Data = xxx;

Class Treatment (param=ref ref='CF2');

model AVAL*CENSOR(0) = baseline_BCVA Treatment/ties=exact;

run;

where CENSOR indicates censored subjects.

In all analyses, data from subject visits after receipt of rescue medication will be imputed using last observation prior to receiving rescue medication for continuous endpoints and will be imputed as failures for success/failure variables.

Additionally, a subset of the efficacy analyses will be performed by combining the initial phase subjects with the randomization phase subjects.

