15.2 Intraocular Pressure

Intraocular pressure will be summarized at each visit, using continuous and discrete summary statistics, including change from baseline and the proportion of study eyes with an increase from baseline in IOP of 10 mmHg or more and the proportion of study eyes with IOP of 30 mmHg or more.

A subject listing of IOP will also be produced. Increase from baseline in IOP of 10 mmHg or more or IOP of 30 mmHg or more will be flagged in the listing.

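### The SAP safety section has no rule for data after rescue, so adverse events and possibly IOP readings that follow another intravitreal treatment count under the AR-1105 formulation received

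*Protocol*

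**What the plan says.** **Event window.** Protocol 9.5: "A TEAE will be defined as occurring after the first dose of study medication". SAP 15.1 (Adverse Events), which supersedes the protocol on methods, counts anything that starts or worsens from treatment onwards and collects events until 30 days after the last visit. Neither text ends or divides the window at rescue. The safety population is grouped by treatment received (Protocol 9.3.1, SAP 7.1).

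**IOP.** The SAP section headed Intraocular Pressure summarizes every visit, including "the proportion of study eyes with an increase from baseline in IOP of 10 mmHg or more" and the proportion at 30 mmHg or more. It does not mention rescue.

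**Rescue.** Protocol 3.1: "Rescue therapy in the form of standard of care will be offered to any subject who, in the opinion of the investigator" needs more treatment for lack of efficacy after Month 3/Week 12. No agent is named or excluded. The Introduction says: "Currently, two classes of medication are approved to treat ME following RVO". It names corticosteroids, such as a dexamethasone implant, and anti-VEGF agents.

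**Rescue in the analysis.** SAP 13.1, in the efficacy chapter, has a sentence that opens by referring to all analyses and continues: "data from subject visits after receipt of rescue medication will be imputed using last observation prior to receiving rescue medication for continuous endpoints". Success/failure variables become failures. SAP section 15 neither repeats nor cites this.

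**Use of the data.** Safety through Month 6, with efficacy signals, decides which formulation goes forward (Protocol 3.1).

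**The concern.** The primary objective is the safety of AR-1105, and the design rationale (Protocol 3.2) is that a lower steroid dose may mean fewer steroid-related events. The Introduction attributes raised IOP and posterior subcapsular cataract to dexamethasone. It attributes endophthalmitis, inflammation, raised IOP and retinal detachment to any intravitreal injection. A rescue injection can therefore produce the same events that the safety tables are meant to describe. The approved dexamethasone implant named there contains 0.7 mg, against a total target of 340 µg in this trial (700/340 = 2.06).

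The plan sets post-rescue data aside for efficacy but says nothing for safety. A pressure rise after a rescue implant could be tabulated as though AR-1105 had caused it. If one formulation is rescued more often, this affects the arms unequally, and the arms are compared in order to choose between them.

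**Working it through.** **1. Which data are exposed**

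| Question | Source | Answer |
|---|---|---|
| When can rescue occur? | Protocol 3.1 | After Month 3/Week 12 |
| Do rescued subjects stay on before Month 6? | Protocol 6.10.1 and 9.6.2, SAP 13.1 | Not stated outright. The rules for visits after rescue presuppose it |
| When does retreatment end participation? | Protocol 7.4 | Stated only for implant follow-up after Month 6 |
| Which IOP summaries are affected through Month 6? | Protocol visit schedule | Scheduled visits at Months 4, 5 and 6 |
| Which event tables are affected? | SAP 15.1 | The cumulative ones, to 30 days after the last visit |
| Is rescue shown beside safety? | SAP 17, 20 and 21 | Discrete rescue summaries are removed. A time-to-rescue table remains. No table or listing of rescue by agent is planned |

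**2. The plan's own safety benchmark**

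Protocol 9.2: "With a sample size of 20 evaluable subjects per treatment group", if an event is not seen, then with 95% confidence "the true incidence rate of that adverse event is less than 13.9" percent. The limit U solves (1 − U)^20 = 0.05, so U = 1 − 0.05^(1/20) = 0.139. The figure reproduces as the one-sided exact limit (the two-sided version would be 16.8%).

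**3. What one more event does to an arm of 20**

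- Crude rate: 1/20 = 5 percentage points per subject.
- One event: (1 − U)^20 + 20U(1 − U)^19 = 0.05 gives U = 21.6%.
- Two events, by the same exact method: U = 28.3%.

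These limits apply to any event, whatever its cause. They show how sensitive an arm of this size is and do not estimate bias.

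**4. Illustrative range for this one mechanism**

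All inputs here are assumptions; the documents give none of them.

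- b = 10%: true event rate from the implant in both arms
- r: proportion rescued, at 10% v 30%, 10% v 50% or 20% v 60%
- s = 25% to 100%: share of rescues that are steroid
- q = 10% to 30%: added event risk after steroid rescue

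The observed rate is b + (1 − b)·r·s·q, so the spurious difference between arms is (1 − b)(r_B − r_A)·s·q.

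- Smallest: 0.9 × 0.20 × 0.25 × 0.10 = 0.0045, about 0.5 points.
- Largest: 0.9 × 0.40 × 1 × 0.30 = 0.108, or 10.8 points.

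The chance of at least one rescue-caused event among 20 is 1 − (1 − r·s·q)^20. It runs from 14% to 98% in the more-rescued arm and from 5% to 71% in the other. The model leaves out any opposing influence.

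**5. What cutting at rescue costs**

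In the extreme case where rescued subjects are not counted at all, the zero-event limit is 1 − 0.05^(1/m) for m remaining subjects:

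- m = 16: 17.1%
- m = 12: 22.1%
- m = 8: 31.2%

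A cut at rescue removes rescue-caused events but also information, and more of it from the arm rescued more often.

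**The case against.** **The imputation rule may already cover IOP.** The SAP 13.1 sentence speaks of all analyses, and IOP is a continuous visit measure. This stands in part. The sentence sits in the efficacy chapter, as its counterpart does in Protocol 9.6.2, so its reach is unclear. It is therefore too strong to say that the SAP plainly leaves post-rescue IOP untouched. On either reading, the sentence imputes visit values and removes no adverse event.

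**Causality tables already separate these events.** SAP 15.1 plans tables of events judged related or possibly related to the study drug or to the procedure, and other therapeutic interventions count as an alternative cause. This helps, especially for an event just after a rescue injection. But the possibly-related category admits events that another treatment could have produced, the judgement is open-label, and IOP readings carry no causality code.

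**With about 20 per arm, timing can be traced in listings.** That is possible from the event, IOP and medication listings. It leaves each reader to build a comparison that the plan could specify.

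**Counting everything after dosing is conventional.** It is, and it should remain the main summary. Stopping at rescue truncates follow-up at a time that depends on outcome and could hide late implant effects. A reader might infer that pre-rescue tables should decide between formulations. For this reason they should not.

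**The trial is small and descriptive, with no planned safety test.** That is true, but its safety data still inform a choice between two arms.

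**Conclusion.** The gap is real. SAP section 15 does not say how safety data after study-eye rescue are treated. As written, adverse events after rescue count under the formulation received, and the position for IOP is ambiguous. If rescue differs by arm, the safety comparison can be distorted. Each affected subject is worth 5 percentage points in an arm of 20, and a first event moves the one-sided limit from 13.9% to 21.6%.

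This rests on two inferences: that standard of care can include the drug classes named in the Introduction, and that subjects rescued before Month 6 keep attending.

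Stronger readings are tempting, but the documents do not support them:

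- That the formulation wearing off sooner will look less safe. No rescue rate is given. A visible implant at Month 6 also brings monthly visits up to Month 9 (Protocol 7.4), which gives the longer-lasting formulation more time to record events. Net direction is unknown.
- That the protocol defines rescue as a steroid or anti-VEGF injection. It says only standard of care; the Introduction lists approved classes.
- That 21.6%, or the 0.5 to 10.8 point range, measures the bias. The first is a generic exact limit and the second depends wholly on assumed inputs.

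**What to change.** In SAP section 15:

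1. Keep the all-data adverse event and IOP tables as the main safety summary, and state that the SAP 13.1 post-rescue imputation does not apply to them.
2. Add supplementary study-eye tables of ocular treatment-emergent events and IOP, limited to onset or readings before first study-eye rescue, with person-time per arm. State how same-day events and readings are classed.
3. Flag post-rescue events and IOP readings in the listings, with the rescue agent.
4. Tabulate rescue by agent and arm, and reconcile SAP 17 item 4, which drops discrete rescue summaries, with SAP 2.2 and 13, which still list the percentage rescued.
5. Say that both sets will be read together for the formulation comparison, and that neither set decides it alone.

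**Cost.** SAP wording, a few extra tables and a date filter. Protocol 6.9 already records drug, route and indication, and SAP 13.1 already derives time to rescue. Protocol 5.6 lets the fellow eye receive standard of care and the Protocol 6.9 list does not mention the eye, so confirm that the treated eye can be identified.

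**Downside.** Exposure in the pre-rescue set is shorter and depends on outcome. That is why person-time is shown and the all-data tables stay primary.
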